#### Revised Study Schema:

Figure 2: Study Schema							
Providers	Recruitment	Screening	Consent	Baseline	Modified DECIDE intervention [workshop ([contact] hrs)]	Time 2	DECIDE Oral Interview (all providers)

**DECIDE Parent-Provider Interaction  
IRB Protocol**

Parents	Recruitment	Screening	Consent	Baseline	Modified DECIDE sessions 2 @ 1 hr/week, with an optional 3 rd booster session offered @ 1 hr/week	Time 2	DECIDE Oral Interview (subset of parents)
Green: Quantitative measures and oral interviews							
All participants will receive the DECIDE intervention. Results will be compared to historical control.							

Training for parents will be delivered remotely using telephone and/or Zoom Health for parents with video capability. The parents will be sent a Zoom Health invitation which include a toll free number they can call. This allows research staff to record sessions for fidelity checks.

**Data collection.** A trained study staff will collect baseline data (T1) before the provider takes the DECIDE Training and will schedule a follow-up assessment 1- 4 weeks post intervention training (T2). Providers will be instructed to think specifically about the most recent therapy session that he/she had with a parent of a child diagnosed with DIC in order to keep the parent provider interaction fresh in the provider's mind when completing the measures. Study staff will follow these same guidelines for scheduling the T2 data collection. Providers will complete and enter their surveys directly into REDCap. Providers will be contacted by study staff to remind them to complete their surveys and to answer any questions if necessary. Study staff will schedule an appointment with providers to collect the post-intervention (T2) measures in order to ensure the provider understands the instructions and also to conduct the post-intervention qualitative interview. Providers will be instructed to think specifically about the most recent therapy session that he/she had with a parent of a child diagnosed with DIC in order to keep the parent provider interaction fresh in the provider's mind when completing the measures. Parents will be contacted and asked to schedule a convenient time to complete the surveys with the study staff.

**Measures.**

**Aim 2 measures.** The research project coordinator will keep logs and field notes of feasibility including: 1) enrollment rates, reasons for ineligibility and declining participation; 2) attrition rate, reasons for missed session or intervention completion; and (3) measurement completion rates. We will measure parent and provider acceptability and satisfaction with modified DECIDE using Client Satisfaction Questionnaire (CSQ) and in-depth semi structured interviews at T2. RAs under [name]'s supervision will conduct in-depth semi-structured interviews including: All intervention providers (n = 8) and two of each of the parents (n = 16). To explore different levels of acceptability by parents, for each provider, one parent will be chosen who has a high score (> 3) on the CSQ and one parent who has a low score (< 3). Both parents and providers will be asked about their experience with the intervention, what was helpful or not, and how they would change the intervention.

**Aim 3 measures.** Parents, providers, and adolescents' socio-demographic factors will be assessed at T1; and outcomes will be assessed at T1 and T2. We will include three items (i.e., level of parent organization, involvement, and management of adolescents' care) from the Child and Adolescent Needs and Strengths (CANS) at Midtown's request. We will use self-administered questionnaires with read-aloud procedures to address issues of literacy. All measures have well-established psychometric properties, sensitivity to change, and acceptable response burden. Multi-informant and mixed methods assessment of outcomes is a study strength. Given the change in design to one group pre and post intervention compared to historical group; we will use the Parent Participation Engagement Measure (PPEM). In lieu of Working Alliance Inventory or Kim Alliance Scale as our key measure of parent-provider interaction or engagement.

**DECIDE Parent-Provider Interaction  
IRB Protocol**

Table 1: Measures					
Variables	Measure	#Items	Reliability (<math>\alpha</math>)	Schedule	Filled By
Antecedents					
Parent Factors	Parent Information Form	10	N/A	T1	Parent
Provider Factors	Provider Information Form	10	N/A	T1	Provider
Adolescent Factors	Adolescent Information Form	7	N/A	T1	Parent
Feasibility/Acceptability					
% Eligible participants enrolled	Investigator Tracking Logs	N/A	N/A	T2	PI
% Eligible participants completed intervention	Investigator Tracking Logs	N/A	N/A	T2	PI
Provider Satisfaction with Intervention	Client Satisfaction Questionnaire; Semi-structured Interview	8; 10	0.93; N/A	T2	Intervention Parent
Parent Satisfaction with Intervention	Client Satisfaction Questionnaire; Semi-structured Interview	8; 10	0.93; N/A	T2	Intervention Provider
Mediators (Target Variables)					
Parent Activation	Parent Activation Measure-Mental Health (P-PAM-MH); Parent Needs and Resource Domain of CANS*	13; 3	0.89; N/A	T1, T2	Parent, Provider
Provider Communication Skills	Communication Subscale of Kim Alliance Scale (KAS)	11	0.94	T1, T2	Parent, Provider
Parent-Provider Interactions	Working Alliance Inventory - Short Form; Audio Tapes	12	0.9	T1, T2	Parent, Provider; Observer
Proximal Outcomes					
Parent Perceived Management of Adolescent Behavioral Health Care	Perceived Efficacy in Parent-Physician Interactions (PEPPI)-Short Form	5	0.83	T1, T2	Parent
Parent Perceived Quality of Adolescent Behavioral Health Care	Perception of Care Survey (POC)	18	N/A	T1, T2	Parent
Parent Engagement in Adolescents' Behavioral Health Care	Parent Participation Engagement (PPE); Proportion of Visits Attended of Scheduled	5; N/A	0.88; N/A	T1, T2	Observer; Medical Record
Distal Outcome					
Adolescent Retention in Behavioral Health Care	Attending at Least 4 visits in 6 Months Post-Baseline	N/A	N/A	T1, T2	Medical Record

\*Midtown specific request; CANS- Child & Adolescent Needs & Strengths

**Compensation.** All parent participants will receive a \$25 gift card for each assessment completed and \$25 gift card if an oral interview is completed. They will receive a \$10 gift card for each training session attended. We will offer continuing education credits (CE) for the 4.5-hr provider workshop. [name] has arranged with her school's Center for Continuing Education and Lifelong Learning to offer the CE credits at minimal cost. Providers will also receive \$100 upon completion of the T1 measures, the DECIDE Workshop, T2 measures and the qualitative interview if located at any center that is not Bowen or Eskenazi.

**Intervention Fidelity.** We will follow the treatment fidelity protocols developed for the original DECIDE trial and the NIH Treatment Fidelity Workgroup recommendations to ensure intervention integrity and minimize drift/group contamination. **Design.** We are comparing an historical control data to intervention data gathered during the study.. Provider training. All study personnel will receive training specific to their role; regular supervision and retraining as needed. We will fully manualize the modified intervention similar to the original DECIDE intervention with standardized treatment protocols, training manuals, and training content, modified from patients to parents of adolescents with DIC. **Treatment Delivery.** Parent and provider intervention delivery will be assessed using a random sample of recorded trainings and checklist of key intervention components. **Receipt and Enactment of Treatment.** Facilitators for parent component will complete a session-specific field note entry that summarizes parent responses (i.e., level of engagement and understanding) and any potential external factors (e.g., interruptions, noise) that may have influenced their response.

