### **3.0 Specific Aims**

The **purposes** of this two-phase study are to modify and test the DECIDE intervention (referred to as DECIDE from now on) for parents and providers of adolescents with DIC. In phase I, our team in Indianapolis, IN (Drs. [name], [name], [name], parent and provider advisory boards) will work with two consultants to modify DECIDE. [name] will help modify the DECIDE provider components to be relevant for DIC. [name] will help modify DECIDE from patient to parent focused. In phase II, we will test modified DECIDE against usual care in parents and providers of adolescents with DIC using a two-group, pilot, randomized, controlled design. During phase II, [name] became a Co-Investigator at the University of South Florida in Tampa, FL. [name] (New York, NY) has clinical expertise in improving activation among parents of adolescents with DIC. [name] (Northampton, MA) led the design and implementation of DECIDE components targeted to providers [name] will help modify DECIDE from patient to parent focused. Our setting is a large, safety net health system in the Indianapolis metropolitan area servicing primarily low income and/or minority persons.

**Specific aims** are to:

**Phase I, Aim 1.** Modify DECIDE for low income and/or minority parents and providers of adolescents with DIC.

**Phase II, Aim 2.** Evaluate the feasibility and acceptability of modified DECIDE.

**Phase II, Aim 3.** Estimate preliminary effects of modified DECIDE to improve parent, provider, and adolescent outcomes. We hypothesize that compared to usual care:

**Hypothesis 3.1.** Modified DECIDE parents will show greater improvements in: 1) activation; 2) parent-provider interactions; 3) perceived management of adolescents' behavioral health care, 4) perceived quality of adolescents' behavioral health care, and 5) engagement in adolescents' behavioral health care.

**Hypothesis 3.2.** Modified DECIDE providers will show greater improvements in: 1) communication skills and 2) parent-provider interactions.

**Hypothesis 3.3.** Adolescents of modified DECIDE parents and providers will show higher rates of retention in behavioral health care.

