### **Study Duration/Timeline**

The study will consist of the provider completing baseline measures and then complete a 4.5 hours (max) workshop through Canvas Learning System, completed over the course of 2-3 weeks. After the provider completes the workshop, he/she will be contacted by study staff to complete the post-intervention measures (T2) and conduct a recorded qualitative interview. The parents will complete baseline (T1) study measures before meeting with the parent trainer. Then all will participate in up to three, hour-long sessions training sessions with a parent trainer. In total, participation in the study will last between 6-8 weeks.

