**Intervention Delivery.** In addition to standard care, all participants will receive the modified DECIDE. Parents receiving intervention will receive up to three 60-minute sessions over the course of three weeks. The sessions will focus on increasing the parent's involvement in decision-making, increasing their understanding of the decision-making process, and training the parents to ask questions concerning their adolescent's care. These training sessions will be delivered by trained study staff virtually via HIPPA compliant video teleconferencing platform (ie Zoom Health) or via Telephone as approved by IRB.

### Phase I, Aim 1

**Recruitment of Parent Advisory Board.** We will form a 5-member parent advisory board to guide modification of DECIDE. Inclusion Criteria. Parents of adolescents with DIC, who are receiving services at Midtown Child and Adolescent Program. We will invite parents sequentially in the clinic as well as parents from our previous study advisory board and who participated in preliminary study 2 that agreed to be contacted for future studies.

**Recruitment of Provider Advisory Board.** We will form a 5-member provider advisory board to guide modification of DECIDE. Inclusion Criteria. Midtown Child and Adolescent Program staffs who do not meet the inclusion criteria in phase II (i.e. manager and clinical coordinators or supervisors). We will invite two other direct care providers who work in the healthcare system but not at recruitment site. No parent or provider will be excluded on basis of race/ethnicity, gender, or sexual orientation.

**DECIDE Modification.** [name] has met both [name] and Midtown Chief Executive Officer, Program manager and clinical coordinators to discuss potential modifications to the provider intervention to increase acceptability and feasibility. We will invite their continued participation during phase I. The research team and provider advisory board will meet monthly for ~ 3 months to modify the intervention. At the initial meeting, the PI will share DECIDE and discuss what components need to be modified. The research team will prepare the modified

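### Adolescent retention is a 6-month outcome scheduled at T1 and T2 of a 6-8 week study; the SAP has no method that fits it and does not say that Hypothesis 3.3 was not evaluated

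*Protocol*

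**What the plan says.** Hypothesis 3.3 (protocol section 3.0) predicts that "Adolescents of modified DECIDE parents and providers will show higher rates of retention in behavioral health care". Table 1 in section 6.0 (Measures, Distal Outcome row) defines retention as "Attending at Least 4 visits in 6 Months Post-Baseline". The source is the medical record, and the schedule column reads T1 and T2. The text on Aim 3 measures gives the same schedule for outcomes in general: "outcomes will be assessed at T1 and T2". Section 5.0 (Study Duration/Timeline) states: "In total, participation in the study will last between 6-8 weeks".

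The timing of T2 for parents is less definite. Under Intervention Delivery, "Parents receiving intervention will receive up to three 60-minute sessions over the course of three weeks". Under Data collection, study staff "will schedule a follow-up assessment 1- 4 weeks post intervention training (T2", but that sentence is built around the provider's training. For parents the same paragraph says only: "Parents will be contacted and asked to schedule a convenient time to complete the surveys with the study staff".

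On analysis, protocol section 9.0 fits linear mixed models to T2 values with the T1 value of the same outcome as a covariate. The SAP says that it departs from that plan because the design became pre/post. It takes the post-minus-pre change, checks normality, and uses a paired t-test or a Wilcoxon signed-rank test. It names three populations (providers, parents, and a second provider group). It reports that parent data were not analysed because only 3 parents had both measurements, and that tests were produced only for the two provider groups. It does not mention adolescents, retention or Hypothesis 3.3.

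**The concern.** The definition and the schedule in one table row cannot both be followed, and the analysis methods assume a before-and-after pair that this outcome does not have. A reader of the results could not tell whether retention was counted over six months, counted over a shorter window, or not examined. A count read at T2 would depend on how often visits were scheduled and when T2 happened to fall, as well as on retention itself. The protocol says that the pilot is meant to supply effect estimates for a later trial, so a rate with an unclear window could be carried forward under the wrong name. A stated hypothesis is also left without a stated outcome.

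**Working it through.** **1. The plan's own figures.** The documents give no rate, power or sample size for retention. The only power figure is an effect size of 0.65 at 80% power (section 6.0, Sample size justification). It reproduces with 40 × 0.8 = 32 per group, correlation 0.5, ICC 0.05 and an assumed 4 completing parents per provider:

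- design effect = 1 + 3 × 0.05 = 1.15
- SD = √((1 − 0.5²) × 1.15) = 0.929
- detectable effect = (1.960 + 0.842) × 0.929 × √(2/32) = 0.650

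That figure is not in dispute. It does not carry over to retention, because it relies on a baseline value correlated with follow-up.

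**2. Window against schedule.** Take 6 months as 26 weeks.

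- Participation of 6-8 weeks (section 5.0): 6/26 = 0.23; 8/26 = 0.31.
- From the parent's baseline, if the provider's 1-4 week interval also applies to parents (an assumption): 3 weeks of sessions + up to 4 weeks = 7 weeks; 7/26 = 0.27.

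**3. What can be known at each time point.**

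| Time | Four or more visits so far | Fewer than four visits so far |
|---|---|---|
| T1 | impossible: the count starts here | true of everyone, uninformative |
| T2 (about 6-8 weeks) | retained, already settled | unsettled: about 18-20 weeks remain |
| 6 months | retained | not retained |

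Only the last row gives the outcome as defined, and no section schedules it.

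**4. Fit of the analyses.** The SAP's variable is post minus pre. With no pre value it is undefined, and a normality check followed by a paired t-test or signed-rank test is not an analysis of a single yes/no value. The section 9.0 model fails for the same reason, because its T1 covariate does not exist. The SAP has in any case replaced that model.

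**5. Fit of the SAP's explanation.** Its reason for omitting parent analyses is that 3 parents had both measurements. Retention comes from the record and needs no T2 survey from the parent, so that reason does not directly cover it.

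**6. Illustration only.** The documents give no visit frequency or attendance rate. Assume fixed visit slots, each attended independently with probability p. Then P(at least 4) = 1 − Σ(k = 0 to 3) C(n,k) pᵏ(1−p)ⁿ⁻ᵏ. At an assumed p = 0.75:

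| Visits | By week 8 | By week 26 | Shortfall |
|---|---|---|---|
| Weekly (n = 8; 26) | 97.3% | over 99.9% | under 3 points |
| Fortnightly (n = 4; 13) | 31.6% | over 99.9% | 68 points |
| Four-weekly (n = 2; 6) | 0% | 83.1% | 83 points |

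For p from 0.5 to 0.9 the week-8 shortfall is 36 to under 0.1 points (weekly), 89 to 34 (fortnightly) and 34 to 98 (four-weekly). The model matters too: a Poisson count gives 57% rather than 32% at week 8 for fortnightly visits, and 14% rather than 0% for four-weekly. These figures show only that the effect could be negligible or large.

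**The case against.** The strongest reply has three parts.

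First, the medical record can be read at any later date, so the schedule entry may be no more than a labelling slip. That may be so, and it means that the outcome is not unmeasurable. But the documents nowhere place a 6-month extraction, and the schedule they do state contradicts one.

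Second, the SAP largely accounts for the matter. It replaces the section 9.0 model, lists no adolescent population, and says that only provider tests were generated. This stands to a large extent: a reader can fairly infer that retention was not tested. What is missing is an explicit statement about Hypothesis 3.3, a reason that applies to a record-based outcome, and word on whether any descriptive count was made.

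Third, this is a pilot whose testing the protocol itself calls exploratory, and the SAP is dated 12/13/2023 and written in the past tense. This also stands, and it limits both the severity and what can still be changed.

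A reader might go further and infer that a biased retention result was produced, or that an unfavourable one was withheld. The documents support neither: they contain no retention figure, promise none at T2, and report no test on it.

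**Conclusion.** The inconsistency is real, and it rests on reading the text rather than on modelling. As scheduled, retention has no T1 value, and non-retention cannot be established at T2 because 6-8 weeks is 23-31% of the window. This does not depend on the exact date of the parent's T2. The current SAP method cannot be applied to the outcome, and the SAP leaves the status of Hypothesis 3.3 to inference.

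Severity is minor. The harm is a hypothesis with no stated disposition and the possibility of a mislabelled rate, not a wrong test result. One might be tempted to size the distortion from the attendance figures. They rest wholly on assumed visit rates, and the week-8 shortfall spans under 0.1 to 98 points, so the size cannot be determined from the documents. The choice of comparator for Hypothesis 3.3 is a separate question, and this conclusion does not rely on it.

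**What to change.** In the retention row of Table 1, replace the T1 and T2 entry with one medical-record extraction covering the 6 months after the parent's baseline, with no T1 value. Report the proportion retained with an exact 95% CI, as descriptive only. State the denominator, meaning families with an accessible record: guardian criterion (f) in section 4.0 admits foster parents whose child is not seen by a participating provider.

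If that extraction was not made, add a sentence to the SAP saying that Hypothesis 3.3 was not analysed and why. Label any count over a shorter window as early attendance, not retention.

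The SAP sentence costs almost nothing, and now that analysis appears complete it is the most practical step. The extraction costs more. It means a later data lock for this one outcome, record access across several centres and private practices, and confirmation that consent covers the adolescent's record for six months. Section 7.0 mentions only administrative data, and the consent pages were not available for this review.

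Precision would be modest. With assumed counts, 24 of 32 (75%) gives an exact interval of 56.6-88.5%, and 2 of 3 gives 9-99% if only the 3 parents counted in the SAP had usable records.

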## 7.0 Reporting of Adverse Events

Participants will be monitored for adverse events on a daily basis. Any adverse events will be reported to PI immediately and IRB immediately. The research investigative team will be responsible for data and safety of this study and include [name], RN (Co-I); [name], RN (Co-I), [name] (PI), [name]

## DECIDE Parent-Provider Interaction IRB Protocol

[name] (Consultant), and [name] (Consultant). In addition to monthly research team meetings, the committee will meet as soon as possible following the occurrence of any adverse events.

*Data.* Parents and providers (participants) in this study will be assigned a participant identification number (PIN). Research materials such as parent and provider interviews will contain the PIN instead of the participants' names. A file containing a link between the PIN and the participants' names will be created and access to this file will be restricted to key research staff such as the Project coordinator and only for the purpose of scheduling interviews. All research staff will be required to complete training in Human Subjects protection sponsored by the Indiana University Office of Research Compliance. This includes basic human subjects' protection and advanced training on Health Insurance Portability and Accountability Act (HIPA) and Conflict of Interest. The staff will also receive additional training on working with participants or handling identifying information.

After obtaining consent from the parent, the research team will access their administrative data, and parent interviews for purposes of this study. Once at research team offices at the university offices, all documents that include identifying information (i.e. names, addresses and telephone numbers) will immediately be separated from the parent assessments, and recordings. These items will be stored by research staff authorized by the PI in a locked file and an identifying case number will be generated. The PI and authorized research staff will be the only persons with access to the locked filing cabinet and/or any information or files that link the case number with any parent identifying information. No reports will be made public using any names or identifying information. Raw data and accompanying research protocols will be kept for at least 7 years post publication of findings, as required by Indiana University. Strict measures to assure confidentiality of the data will be taken. Computerized data will be identified by participant number only. All research staff PCs are password-protected and have standardized, full featured, software and hardware configurations. Only research staff authorized by the PI will have access to the data.

Data analysis will be conducted with use of coded data to reduce the chance of inadvertent disclosure. [name] and her statistical team working with the data are the only persons on-site with network level administrative password privileges. The original data and the encrypted data will not be transported or used at any other location and the data will not be copied onto other computers, discs, CDs etc. We will maintain all print-outs, electronic files, personal computers with restricted data on the hard drives, or other physical products containing data in locked cabinets, file drawers or other secure locations when not in use. Printed material that includes analyses based on restricted data will be promptly destroyed. At the end of the project, all files that include restricted data will be destroyed, including copies and subsets on the Indiana University server or any project computers.

*Safety.* The committee will monitor adverse events reported by participants and reasons for dropping out. Adverse events will be reported to the study PI or her designee within 24 hours, and any serious unexpected adverse events related to the study intervention will be reported to the Institutional Review Board within 5 working days. The relationship between adverse events and the study intervention will be determined based on PI and her research staff examination of the subject (research staff and/or patient) and subsequent clinical judgment. Both provider and parent participants will have several phone numbers to call should they have any concerns or questions about any aspect of the study, including contact numbers for the PI, the project coordinator, the IRB offices, and the parent/patient representatives at Midtown. All other adverse events will be reported annually with the continuing review. Study Withdrawal/Discontinuation. Taking part in the study is voluntary. A participant may choose not to take part in the study or to withdraw from the study at any time. If the participant withdraws from the study, he/she will not be penalized in any way and will not lose any benefits he/she is entitled. The participant may choose to contact the study PI to formally withdraw, or he/she may simply choose to stop coming to the study sessions. If the participant chooses to withdraw, a study representative will call the participant to make sure he/she is ok. The study representative will provide the participant with contact numbers to obtain other resources. For example, parents may be provided number to other Midtown programs or National Alliance on Mental Illness (NAMI) Indianapolis. In addition, the PI will meet monthly with the research project coordinator to review data collected to date in order to determine if there are any major problems in data collection procedures or data collected.

